9.3 Blood sample handling /temporary storage and testing

Following notification by the electronic identification process, left-over EDTA and citrate blood samples from potentially eligible patients (which were taken as part of normal clinical care) will be transferred to a dedicated `holding area` in the MRC Weatherall Institute of Molecular Medicine (WIMM).

Prior to consent being sought, all sequestered left-over samples will undergo processing to extend their viability for later analysis. This will occur in the holding area. The processing will consist of:

- Citrate samples will be spun down and the plasma and buffy coat will be aliquoted off into separate tubes
- Any remaining serum from a sample will also be aliquoted off

Samples will be processed, frozen and retained by the WIMM (The MRC Weatherall Institute of Molecular Medicine) laboratory in a dedicated area allocated to only this study. The samples will be labelled with the study ID number. Samples will be held (without consent) for a total of 28 days from the time they were taken, to maximise the time and opportunity for the study team to formally consent patients for use of these samples in the study.

Members of the study team will liaise with the clinical care team who will approach the patient and if appropriate introduce the trained study team member. The study team member will then explain the purpose of the study and seek the patient's consent. If consent is obtained, the laboratory will be notified that the sample can be retained until the end of the study. If the patient does not consent, the laboratory will be notified to destroy the sample in line with local policies.

If written consent has not been obtained after 28 days from the bleeding episode all samples will be destroyed in line with local policies.

Where consent is provided, plasma samples will be analysed for haemostatic potential using:

- Standard clotting analysis: Prothrombin time (PT) and activated partial thromboplastin time (APTT) (if not already performed as part of the clinical care), clot lysis, thrombin generation, clotting factor levels and the contributing role of platelet factors.
- Fibrinogen concentration

- Endothelial cell markers: Thrombomodulin & syndecan-1

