9.4.3 Patients with capacity to consent

Formal written consent will be sought from a subset of patients to analyse surplus clinical blood samples. This will be conducted by group of experienced research nurses.

Patients with the physical and mental capacity to give informed consent will be approached in person during the first 28 days following their episode of bleeding and it will be explained to the patient that they have already had blood samples sent for storage. It will be made clear that these samples have not yet been analysed and that these samples will be destroyed if they do not agree to the samples being used.

For any patient where a sample was retained with the intent to be used in the study but the patient did not regain capacity within 28 days, information will be provided to either a personal or a professional consultee for advice about the research use of the sample (see next section).

After this period has past, if consent has not been obtained, all samples will be destroyed.

Patients or their personal or professional consultee will be provided with:

- RE-BLEED patient information leaflet
- RE-BLEED consent form

The RE-BLEED study documentation will detail no less than: the nature of the study; what it will involve for the participant; the implications and constraints of the protocol; the known side effects and any risks involved in taking part. It will be clearly stated that the participant is free to withdraw from the study at any time for any reason without prejudice to future care, without affecting their legal rights, and with no obligation to give the reason for withdrawal.

The participant or consultee will personally sign and date the latest approved version of the Informed Consent form or Consultee Declaration.

The participant, or their consultee, will be allowed a maximum of 28 days to consider the information, and the opportunity to question the Investigator, their GP, or other independent parties to decide whether they will participate in the study.

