Written Informed Consent will then be obtained by means of participant-dated signature (or consultee dated signature) and dated signature of the person who presented and obtained the Informed Consent/Consultee Declaration. The person who obtained the consent will be suitably trained and will have been authorised to do so by the Chief Investigator. A copy of the signed Informed Consent/Consultee declaration will be given to the participant. A copy will be added to the medical notes. The original signed form will be retained at the study site.

[figure not shown]

Figure 1 - Consent flow chart

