9.4.4 Patients without capacity to consent

Patients who experience an episode of bleeding may transiently experience a lack of capacity to consent, either due to the bleeding itself or the resulting treatment. Bleeding also occurs in those who already lack capacity or in patients who may lose capacity as a result of the event (i.e. trauma with brain injury).

This is a feasibility study trialling a consent model designed to be used in a subsequent interventional trial, of patients during a bleeding episode. A future trial would include randomisation to an intervention, as well as sequestering all available blood samples. Our consent model must be able to include those who lack capacity at the time of bleeding in order to be able to offer an effective future intervention. It is essential that any future study does not exclude those who either had a temporary or permanent lack of capacity, as this would both introduce bias into the study but also deprive the most vulnerable and severely affected from a chance to participate in a study.

Capacity to consent to this study, will be assessed by the clinical team looking after the patient and confirmed by members of the study team. For patients lacking capacity, a personal or professional consultee will be approached.

If a personal consultee is not available, a professional consultee will be consulted. For the purpose of this study, a professional consultee is defined as a clinician (qualified doctor or registered nurse) with

appropriate training (according to local Trust policies) to take on the role of professional consultee. Professional consultees must not be directly involved in the patient's care and cannot be a member of the core study team at site.

If a consultee declines to give consent/advice for the samples and any associated sample data to be retained in the study at any stage, his/her wishes will be respected. A consultee is free to withdraw their support for continuation in the study at any time.

Participants where a consultee has been sought will be visited regularly during their admission, including just prior to discharge. If capacity is regained at any point, then informed consent will be sought. If the patient chooses not to provide consent data and samples will be destroyed. If capacity is not regained, then the samples and data will be included in the planned analysis.

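### Section 9.4.3 turns to a consultee only at the 28-day limit at which unconsented samples are destroyed, and Section 9.3 counts those 28 days from two different dates

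*Protocol*

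**What the plan says.** Four sections of the protocol bear on the timing.

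- **9.4.3, approach.** Patients with capacity "will be approached in person during the first 28 days following their episode of bleeding". This is the only start point that the section names.
- **9.4.3, consultee.** Where a sample was retained and "the patient did not regain capacity within 28 days, information will be provided to either a personal or a professional consultee for advice", the reader is sent on to 9.4.4. The next sentence reads "After this period has past, if consent has not been obtained, all samples will be destroyed". Later in the section, the participant or consultee "will be allowed a maximum of 28 days to consider the information". Consent is documented as follows: "Written Informed Consent will then be obtained by means of participant-dated signature (or consultee dated signature"), so a consultee's signature is one of the accepted means.
- **9.3, holding and destruction.** One sentence says "Samples will be held (without consent) for a total of 28 days from the time they were taken". A later one says "If written consent has not been obtained after 28 days from the bleeding episode all samples will be destroyed in line with local policies".
- **9.4.4, no capacity.** "For patients lacking capacity, a personal or professional consultee will be approached". These patients are then visited through the admission, their own consent is sought whenever capacity returns, and the samples are analysed if it does not.
- **9.6, patient involvement.** The process described to the patient group goes to the patient first, once competent, and to a personal consultee if that does not happen.

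**The concern.** The condition that opens the consultee step in 9.4.3 can be known to be met only when the 28 days are over. At that same point, 9.4.3 and 9.3 have the sample destroyed unless consent is in hand. Followed literally, these rules ask a consultee about a sample that is already due for destruction. Staff who follow 9.4.4 with an early approach could keep the sample of the same patient.

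This touches the purpose of the study. Section 9.4.4 presents the study as a trial run of a consent model that has to cover patients without capacity when they bleed. The number of samples retained is a secondary outcome (Section 6, item 6). A rule that discards samples from patients with prolonged incapacity would lower that count because of how the protocol is worded, and would say nothing about feasibility.

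The two start points in 9.3 are a second, smaller problem. They give different destruction dates for any sample taken after the bleed.

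**Working it through.** The protocol gives no figure to reproduce, so the check is a day count plus a comparison of the sections. Day 0 is the bleeding episode, as in 9.4.3 and in the destruction sentence of 9.3.

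**Inputs**

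- Consultee trigger in 9.4.3: T = 28.
- Destruction limit counted from the bleed (9.3): D1 = 28. The period in the destruction sentence of 9.4.3 is not defined, but 28 days is the only period named before it.
- Holding limit counted from sampling (9.3), for a sample taken k days after the bleed: D2 = 28 + k. The protocol does not give k; 1, 3 and 7 are illustrative.
- Maximum consideration time (9.4.3): R = 28.
- Day of consultee approach under 9.4.4: c. The protocol does not give c; 3, 7 and 14 are illustrative.

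**Step 1: time left under 9.4.3.** D1 - T = 28 - 28 = 0 days.

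**Step 2: latest permitted advice under 9.4.3.** T + R = 28 + 28 = day 56, which is 56 - 28 = 28 days after the limit counted from the bleed.

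**Step 3: time left under 9.4.4 if the consultee is approached on day c.** D1 - c = 28 - c.

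| c | Days left before day 28 |
|---|---|
| 3 | 25 |
| 7 | 21 |
| 14 | 14 |

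An early approach leaves usable time. The full consideration period still fits only if c = 0, because c + 28 exceeds 28 for any later approach.

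**Step 4: the two start points in 9.3.** D2 - D1 = (28 + k) - 28 = k.

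| k | Limit from the bleed | Limit from sampling | Days left for a consultee first approached on day 28 |
|---|---|---|---|
| 1 | day 28 | day 29 | 0 or 1 |
| 3 | day 28 | day 31 | 0 or 3 |
| 7 | day 28 | day 35 | 0 or 7 |

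The two limits agree only for k = 0.

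**Step 5: order of steps.** Section 9.4.4 gives no day for the consultee approach. It does have patients with a consultee followed for a later return of capacity, which makes sense only if the consultee was approached before the outcome on capacity was known. Section 9.4.3 puts the consultee after 28 days without capacity. Section 9.6 also puts the patient first, without a day limit. The cross-reference from 9.4.3 to 9.4.4 therefore leads to a different implied sequence.

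**The case against.** The strongest reply is that 9.4.4 governs patients without capacity. Section 9.4.3 is headed for patients with capacity, and its one sentence on the others points onward. If staff approach a consultee early and obtain a signature before day 28, that signature is an accepted means of written consent, the destruction sentences do not apply, and 9.3 and 9.4.4 agree. This stands, and it limits the reach of the point. It does not remove the sentence in 9.4.3 that sets a different trigger.

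The result of 0 days also depends on the limit counted from the bleed; counted from sampling, k days remain. That is correct, and it is a consequence of the two start points. Figure 1, the consent flow chart, is not available here and may show the intended order. Even so, it would not make the written sections agree.

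Three stronger readings are tempting, and the document does not support them:

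- A reader might infer that 9.4.4 orders an immediate consultee approach. It states no timing; an early approach is only implied.
- A reader might infer that the fault lies in the 9.4.3 sentence alone. Section 9.6 also describes a patient-first order, although it reports a discussion and sets no 28-day rule.
- A reader might infer from 9.6, which expects most or all patients to lack capacity at presentation, that the primary outcome is at risk. Incapacity at presentation is not incapacity at day 28, and the latter share is not given.

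Whether a consultee declaration counts towards the 40 is a separate question of outcome definition. An analysis plan could settle it, and it is not part of this point.

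**Conclusion.** The contradiction is real and limited in reach. Read literally and counted from the bleed, 9.4.3 and 9.3 leave 0 days for consultee advice in patients who are first referred to a consultee at day 28, against a stated maximum of 28 days to consider. Section 9.4.4 implies an earlier approach without stating one.

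The consultee conflict concerns only patients still without capacity at day 28 who have no earlier consultee signature. Patients who regain capacity and consent in time, or whose consultee signs earlier, are unaffected. The protocol gives no basis for sizing the group, so no effect on the 40 of 200 can be computed.

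The difference in start points is k days for a sample taken k days after the bleed and zero for one taken on the day. It matters only where written consent is still missing at the earlier limit.

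The conclusion assumes that the undefined period in the destruction sentence of 9.4.3 is the 28 days named before it, which 9.3 supports. The values of c and k are illustrative. The point should be corrected because a stated rule, if followed, removes samples that the consent model is meant to be able to include.

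**What to change.** Reconcile Sections 9.3, 9.4.3, 9.4.4 and 9.6 on when a consultee is approached. The revised text should do one of two things: let the consultee step, including its consideration period, be completed before samples are destroyed, or have destruction wait while advice is pending. Which sequence applies is for the sponsor to decide and state.

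Use a single start point for the 28 days throughout 9.3 and 9.4.3, and say how the consideration period relates to the retention limit. Check that Figure 1 shows the same sequence.

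The cost is a short protocol amendment with the usual ethics submission. Depending on the sequence chosen, some consultees may have to be approached earlier or some samples held longer.

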9.4.4 Patients without capacity to consent

Patients who experience an episode of bleeding may transiently experience a lack of capacity to consent, either due to the bleeding itself or the resulting treatment. Bleeding also occurs in those who already lack capacity or in patients who may lose capacity as a result of the event (i.e. trauma with brain injury).

This is a feasibility study trialling a consent model designed to be used in a subsequent interventional trial, of patients during a bleeding episode. A future trial would include randomisation to an intervention, as well as sequestering all available blood samples. Our consent model must be able to include those who lack capacity at the time of bleeding in order to be able to offer an effective future intervention. It is essential that any future study does not exclude those who either had a temporary or permanent lack of capacity, as this would both introduce bias into the study but also deprive the most vulnerable and severely affected from a chance to participate in a study.

Capacity to consent to this study, will be assessed by the clinical team looking after the patient and confirmed by members of the study team. For patients lacking capacity, a personal or professional consultee will be approached.

If a personal consultee is not available, a professional consultee will be consulted. For the purpose of this study, a professional consultee is defined as a clinician (qualified doctor or registered nurse) with

appropriate training (according to local Trust policies) to take on the role of professional consultee. Professional consultees must not be directly involved in the patient's care and cannot be a member of the core study team at site.

If a consultee declines to give consent/advice for the samples and any associated sample data to be retained in the study at any stage, his/her wishes will be respected. A consultee is free to withdraw their support for continuation in the study at any time.

Participants where a consultee has been sought will be visited regularly during their admission, including just prior to discharge. If capacity is regained at any point, then informed consent will be sought. If the patient chooses not to provide consent data and samples will be destroyed. If capacity is not regained, then the samples and data will be included in the planned analysis.

9.5 Description of study intervention(s), comparators, and study procedures (clinical)

This is a non-interventional study. The algorithm within the Digital Platform will identify potential patients with acquired bleeding, of any severity. Once the cohort has been identified, they will be approached to consent for research use of their surplus clinical sample.

9.6 Patient Public Involvement (PPI)

PPI engagement remains integral to this project. The main ethical issue arising from this study is the use of patient information from Oxford University NHS Foundation Trust without consent.

A virtual PPI meeting was held on 14th December 2020, between the study team and the PPI group which included patients who have suffered significant bleeding, their carers, and members of the public. The meeting focused on two specific issues relating to consent: a) we explored the acceptability of using patient identifiable data in this study without consent and b) the use of personal and nominated consultees for advice about blood samples being stored and later analysed.

The members of the PPI group recognised that patients who are suffering from acute blood loss are likely to require rapid and emergent care. Further, the majority, if not all of the participants we would like to enrol in this study will be incapacitated at the time of presentation and routine blood sample collection, due to several factors - including in some cases acute circulatory failure or the need for urgent care and intubation. The PPI group unanimously agreed that data collection for this patient group was acceptable without consent. They were keen to know that patients would not be identifiable by the data that were collected.

A second question of retaining surplus clinical blood samples for research analysis was also explored. Within this study the researchers would like the samples to be retained for them, pending consent from the patients. We would then follow a strict consenting protocol (as set out above and which was explained to the PPI group) which would involve approaching the patient once they had regained competence to provide informed consent, or if this were to not happen to approach a personal consultee. Again, there was unanimous agreement within the PPI group that this route of consenting was acceptable. We discussed approaching relatives for agreement if a patient died and they were

comfortable in general with this, although recognised that a professional consultee could also be used. They were accepting of the option of gaining agreement from an independent professional consultee, although were clear that this route should be 'the last resort'.

The Oxford University Hospitals NHS Foundation Trust patient facing website and privacy notice state that "Information may be used for approved research projects. In most instances the information will be made anonymous so that you cannot be identified. If this is not possible, we will ask your permission or request approval from the Health Research Authority's Confidentiality Advisory Group. If you are not happy with information about you being used in research projects, please speak to your clinical team".

We commit to ongoing PPI/PPIE involvement throughout the lifecycle of the study.

9.7 Early Discontinuation/Withdrawal of Participants

During the course of the study a participant may choose to withdraw at any point.

The patient information sheet and study website will all carry contact details for the study team.

According to the design of the study, participants may have the following two options for withdrawal:

- Withdrawal from screening: Data will be destroyed from the study database
- Withdrawal of consent obtained in prospective recruitment: Data will be destroyed from the study database and the samples destroyed (if applicable).

9.8 Definition of End of Study

The end of study is the point at which all the study data has been entered and queries resolved.

10 SAFETY REPORTING

This is a non-interventional study and at no point will clinical care be modified or affected by the study.

11 STATISTICS AND ANALYSIS

The statistical aspects of the study are summarised below. A statistical analysis plan (SAP) that will be available from the time that the last participant is recruited. The SAP will be finalised before any analysis takes place.

11.1 Description of the Statistical Methods

11.1.1 The plans for the statistical analysis of the study are outlined below. assessed using descriptive statistics. Variables

The following variables will be extracted for each patient admission in the retrospective and prospective cohorts:

- Laboratory data
 - Biochemistry/haematology/transfusion/coagulation data
- Demographics
 - Age, sex, type/site of bleeding
- Prescriptions on admission and through hospital stay
 - Anti-platelets, anti-coagulants etc.
- Vital signs
 - Blood pressure, heart rate, temperature, respiratory rate, level of consciousness (AVPU/GCS), oxygen therapy, sedation (if applicable)
- Procedures as treatments for bleeding:
 - Surgery/Interventional radiology/need for massive transfusion/haemostatic agents/tranexamic acid/uterotonics if obstetric
 - Treatments for VTE
- Prevention (to include IVC filter)
- Treatments
 - If treated pre-hospital, any features of monitoring (e.g. blood pressure) and time from injury to arrival in hospital and interventions (such as tranexamic acid or fluid infusion or blood transfusion).
- Blood sample data / laboratory feedback
 - Number of blood samples successfully retained
 - Number of additional clotting data points obtained via testing the retained samples
 - Challenges faced by the laboratory team during sample retention

11.1.2 Descriptive statistics

We will calculate summary statistics (e.g. demographics, treatments, mortality,) for both the retrospective and prospective cohorts identified by the algorithm.

For continuous variables we will use the median/interquartile range; for binary or categorical variables we will use the proportion. Confidence intervals for proportions were calculated using the Pearson-Klopper method. We will be able to make compare event rates with previously published data (UK, USA, Europe).

